### Feedback

---

## Protocol Renewal Form

### Renewal Information

## Protocol Type

### **Are you submitting a renewal for an IRB, sIRB, or hSCRO protocol?**

IRB (UCI is the IRB of Record)

---

## IRB Renewal Instructions

### Timing of Submission

Exempt and Expedited IRB protocols must submit a short version of the renewal every three (3) years unless determined otherwise by the IRB. Investigators should plan ahead and submit 60 days prior to the study's expiration date.

Full Committee IRB protocols must submit a renewal at least annually (not more than 365 days). Investigators should plan ahead to meet required continuing review dates. For full committee review protocols, please submit 90 days prior to the expiration date to guard against a lapse in IRB approval.

### Amendments at the Time of Renewal

Please **refrain from making major changes** during the renewal as this could result in a lapse of IRB approval.

### Protocol Closure

To close out an approved protocol at the time of renewal, the transaction must be submitted as Request Close. If this option was not initially selected and closure is required, please Abandon the draft and start again. For more information, visit [Post-Review Responsibilities](#) and select the Protocol Renewal Tab.

## Renewal Screener

Does any of the following apply to the currently approved protocol:

- research involves Greater than Minimal Risk (Full Committee)
- research is subject to **Food and Drug Administration (FDA) regulations**
  - Involves a drug
  - A clinical investigation of a medical device
- research is funded/supported by the Department of Justice (DOJ)
- current approval period is 1 year or less

Yes (Continuing Renewal Required)

### Protocol Expiration

## Protocol Expiration

Has approval for this protocol expired or will it expire within 3 weeks?

No

### Confirmation of Protocol

## Study Team

Review the Study Team Section and consider whether anyone should be removed at this time via an Amendment.

## RP Heat Map

**Are RP tracked outside the approved protocol, in accordance with the RP Heat Map?**

Yes, RP are tracked on a Study Team Log or other comparable log

## Financial Interests

**Review the Study Team section and specify below if there have been any changes in the study team's related financial disclosable interests.**

See [Conflict of Interest Oversight Committee \(COIOC\)](#) for more details.

No, there have been no changes to the study's teams related disclosable financial interests

## Relying Non-UCI Entity (as applicable)

**When UCI is the IRB of Record for a non-UCI entity (i.e., site or independent investigator), review the sIRB section and remove any non-UCI entities (site or independent investigator) that are no longer *engaged in research* via an Amendment.**

---

Clinicaltrials.gov Status

## [ClinicalTrials.gov Registration](#)

**Does this research meet the definition of a [clinical trial](#) that requires adherence to [Clinicaltrials.gov](#) (CT.gov)?**

Yes

## **Confirm the accuracy of ClinicalTrials.gov section in the IRB protocol (**select one**):**

Please review the ClinicalTrials.gov section in the IRB protocol to verify that the information is still accurate.

If any revisions are required, please submit an amendment to request a 'Change in Clinicaltrials.gov' and update the the protocol accordingly.

As lead researcher, I confirm that the CT.gov information is accurate as indicated in the protocol

## **Specify who is responsible for registering, maintaining, and updating the CT.gov record:**

UCI Investigator

## Confirm the accuracy of the information on the ClinicalTrials.gov Protocol Registration and Results System (PRS):

**IMPORTANT!** Per federal requirements (42 CFR 11.64(a)(1)(ii)), clinical trial registration information on PRS must be updated not less than once every 12 months.

Please review the [information on PRS](#) to verify that the following fields are accurate and up to date:

- **Study Status:**
  - **Record Verification Date:** Not less than every 12 months, enter the date on which the responsible party last verified the clinical study information on PRS, even if no additional or updated information was submitted.
  - **Overall Recruitment Status:** 30 calendar days after a change in overall recruitment status, enter the status for the clinical study as a whole, based upon the status of the individual sites. If at least one facility in a multi-site clinical study has a status of "Recruiting," then the overall status for the study must be "Recruiting."
  - **Primary Completion Date:** 30 calendar days after the clinical trial reaches its actual primary completion date, enter the date that the final participant was examined or received an intervention for the purposes of final collection of data for the primary outcome, whether the clinical study concluded according to the pre-specified protocol or was terminated. In the case of clinical studies with more than one primary outcome measure with different completion dates, this term refers to the date on which data collection is completed for all of the primary outcomes. **IMPORTANT!** This date cannot be in the past, please revise the date as necessary.
  - **Study Completion Date:** 30 calendar days after the clinical trial reaches its actual study completion date, enter the date the final participant was examined or received an intervention for purposes of final collection of data for the primary and secondary outcome measures and adverse events (for example, last participant's last visit), whether the clinical study concluded according to the pre-specified protocol or was terminated. **IMPORTANT!** This date cannot be in the past, please revise the date as necessary.
- **Oversight:**
  - **Human Subjects Review Board Status:** 30 calendar days after a change in status, ensure the status of IRB approval information is accurate.
- **Contacts, Locations, and Investigator Information:** 30 calendar days after a change, ensure the information is accurate.

As leader researcher, I confirm that the clinical trial information (listed above) on PRS is accurate and up to date.

## Enrollment Status

### Accruals

**Please mark the option that represents the current status of subject enrollments:**

Enrollment and research procedures complete - only access to identifiable data / data analysis ongoing

### Subject Enrollments

**Please confirm the total number of subjects (i.e. individuals, specimens, records) approved by the UCI IRB in the Subject Populations section.**

**Indicate the number of new subjects enrolled since last IRB review:**

2

**Indicate the total number of subjects (including the number in the previous question) enrolled since initial UCI IRB approval:**

2

**Did the total number of subjects enrolled to date exceeds the total number approved by the IRB?**

No

**Indicate the total number of subjects enrolled per group since initial IRB approval:**

**Man (total):**

22

**Woman (total):**

15

**Nonbinary (total):**

0

**Not Collected (total):**

0

**Adults (total):**

37

**Minor (total):**

0

**Multi-Center Studies: If known, indicate the total number of subjects enrolled at ALL sites to date:**

For Rancho Los Amigo Rehab Center: 10 Males and 2 Females - total of 12 participants. For Casa Colinas Rehab Center: 10- males, 13 females - total of 23 participants

---

### Subject Withdrawals

#### Early Termination(s)

**Did the Lead Researcher or a Co-Researcher remove any subject(s) from the study?**

No

#### Voluntary Withdrawal(s)

**Did any subject(s) voluntarily withdraw from the study?**

No

---

## Reportable Events

### Reportable Events

**Have there been any problems that required prompt reporting to the UCI IRB?**

No problems that require reporting

### Complaints

**Have there been any complaints from UCI participants or others that required reporting to the UCI IRB?**

No

## Progress Report

### UCI Progress

**Please provide a detailed description of the progress of the study, including a brief summary of any interim findings or trends, and plans for the next approval period:**

We have completed our recruitment and enrollment for our study. All study procedures and follow up assessments have been completed. We are in the process of performing data analysis and manuscript preparation.

### Relying Entity Progress (as applicable)

**If UCI is the IRB of Record for a non-UCI entity, provide a progress report for each relying entity (e.g., number of participants enrolled at the sub-site; data analysis performed, if any, etc):**

0

**Sponsor Multi-Center Progress (as applicable):**

**Is a multicenter progress report / newsletter is available from the Sponsor?**

No

**Provide any available information related to multi-center progress from the Sponsor:**

We are in the process of data analysis and will generate a final report and manuscript from the study.

---

**Internal and External Audits****Internal Audit(s)**

**Have any internal (UCI/UCI Health) audits occurred since last IRB review?**

No

**External Audit(s)**

**Have any external (FDA/OHRP/Sponsor) audits occurred since last IRB review?**

No

---

**Risk and Safety Assessments**

## **Relevant Recent Literature**

**During the past year has there been anything in relevant literature that the IRB should consider when reviewing this application for continuing approval?**

No

## **Current Risk/Benefit Assessment**

**Has there been a change in risk/benefit?**

Take into account the information gathered during the past year such as interim results, reportable events/problems, changes in scientific knowledge, and/or relevant regulatory actions regarding study-wide safety and/or efficacy (e.g., product recall). This assessment should be sufficiently detailed to assist the IRB in determining whether continuation of IRB approval is appropriate.

No

## **Data Safety Monitoring Board (DSMB)**

**Has there been any new DSMB findings relating to subject safety?**

Not applicable

## **Investigator's Brochure (IB)**

**For FDA regulated drug studies, enter the current version number and date of the Investigator's Brochure in the Supplemental Documents section.**

**End of renewal form!**

**IMPORTANT!** Go to the next section to complete the amendment form.

---

## Protocol Amendment Form

### Amendment Instructions

#### Specify the type of submission:

RENEWAL: This is a renewal that does not require changes to the approved protocol

---

### End of amendment form!

---

### Project Details

#### Project Title (**100 words max**):

Comparing different rehabilitation exercise strategies for improving arm recovery after stroke

#### Lead Unit (i.e., Department, Organized Lead Unit, **Center or Institute**):

\*\*\*IR-7455 - NEUROLOGY (Lead Unit)\*\*\*

Kuali Research (KR) follows the [KFS Organizational Unit Hierarchy](#).

**ATTENTION!** For **new submissions**, Department Chair (DC) or Organized Lead Unit Director (OLUD) sign-off in KRP is required before final committee approval will be granted. For more information, visit the [listserv](#).

## Submission Screener

### Submission Type:

**IMPORTANT!** Be sure to select the correct 'Submission Type'. When '**Submission Type**' is **changed, the contents of the form will be cleared** and replaced with a set of new questions specific to the submission type.

Institutional Review Board (IRB) Review

### Lead Researcher's primary **school/department/program** is:

Biomedical (Health Sciences)

### Select the **level of review** for this protocol:

Greater than Minimal Risk (Full Committee)

### Is this expanded access, humanitarian use device, or right to try?

Not applicable

### Specify who initiated/authored the project:

Investigator

### Is this study an extension of a UCI IRB approved study (e.g., resubmission of ongoing exempt research; open label extension) or is it otherwise related to a UCI IRB approved study?

No

## Supplemental Documents

## Does this study include a Sponsor's Master Protocol (MP) or detailed project proposal?

No

### Project Funding

#### Select the funding source(s) (**check all that apply**):

Grant/Contract

#### Select the sponsor type(s) (**check all that apply**):

National Institutes of Health (NIH)

### Clinical Trials

#### Is the research a *clinical investigation*?

A *clinical investigation* is any experiment that involves a *test article* and one or more *human subjects*, and that meets any one of the following:

- Any administration of approved drugs for research purposes that is not according to their approved indications, route of administration, population, or dose
- Any activity that evaluates the safety or effectiveness of a medical device
- Any activity the results of which are intended to be later submitted to, or held for inspection by, the FDA as part of an application for a research or marketing permit

An individual becomes a *human subject* for FDA purposes if their data or specimens are used as the recipient of the test article or control. For example, when retrospective data are used as the control, the individuals become human subjects. Likewise, when an individual's blood sample is used to test an assay, the individual becomes a human subject.

Yes

Clinicaltrials.gov

Registration on ClinicalTrials.gov may be required if one (or more) of the following is true:

- Study meets the definition of an Applicable Clinical Trial (ACT) ([ACT Checklist](#))
- Study is NIH funded and meets the [NIH definition](#) of a clinical trial
- Study is DoD funded and registration is [required by your specific program](#)
- Study meets the International Committee of Medical Journal Editors ([ICMJE definition of a clinical trial](#))
- Study includes reimbursement of [Medicare](#) claims

Does this research meet the definition of a **clinical trial** that requires adherence to [Clinicaltrials.gov](#) (CT.gov)?

Yes

Specify the rationale for CT.gov registration (**check all that apply**):

NIH funded clinical Trial

Provide the CT.gov registration NCT # (Enter 8-digit sequence of numbers only):

NCT05880940

**ATTENTION!** All clinical trials initiated at the School of Medicine (SOM) must be performed under the auspices of an Organized Lead Unit (OLU).

Go to Project Details and choose the appropriate OLU for the trial.

## Scientific/Scholarly Review

Investigator-authored research involving greater than minimal risk to subjects (full board review) requires scientific/scholarly merit prior to IRB review - with few exceptions.

The following options identify the scientific merit process for the proposed research and the order of IRB review. Researchers should work with their Departments and the applicable committee (e.g., PRMC) to coordinate the review of their projects, as necessary.

The proposed research qualifies as greater than minimal risk, investigator-initiated biomedical research.

**REQUIRED!** Review from the Biostatistics, Epidemiology and Research Design (BERD) unit of the Institute for Clinical and Translational Science (ICTS) is required. The UCI IRB staff will coordinate the review in conjunction with the expertise of the BERD.

Please click on the following link to arrange a consultation with one of the ICTS BERD Statisticians: [ICTS BERD Statisticians - Consultations](#).

## Is the research cancer-related?

No

### Other UCI Committee Reviews

Research involving human subjects sometimes requires the approval or authorization of [Other Reviews Required by UCI \(e.g., School of Medicine Review Committees\)](#).

Additional Review by the following Committees *may* be required prior to IRB review:

- [Human Stem Cell Oversight \(hSRCO\) Committee](#)
- [Institutional Biosafety Committee \(IBC\)](#)
- [Radiation Safety Committee \(RSC\)](#)

For a list of all ancillary committees, their requirements and how they relate to the IRB review process, refer to the [Other UCI Required Reviews Chart](#).

### Potentially Hazardous Materials

Specify if any of the following hazardous materials are used for **research-related purposes** (i.e., not for standard of care) (**check all the apply**):

Not Applicable

**Are RP tracked outside the approved protocol, in accordance with the [RP Heat Map](#)?**

Yes, RP are tracked on a Study Team Log or other comparable log

---

**sIRB Screener**

**Is a non-UCI investigator and/or their site [engaged](#) in human subjects research activities (e.g., interact with subjects; have access to identifiable information)?**

No

---

**Non-Technical Summary**

**Provide a non-technical summary of the project that can be understood by non-scientists (250 words max):**

Stroke is a leading cause of chronic disability with 6.8 million survivors currently living in the United States, and an annual cost over \$50 billion. An estimated 40% of people with a stroke live with moderate to severe impairment of their upper extremity [1-3]. One likely reason the percentage of people who end up with nonfunctional arms is so disappointingly high is that the number of arm movement repetitions provided as part of standard of care rehabilitation therapy is very small, especially early after stroke during their heightened period of brain plasticity. This is in part because practicing rehabilitative movements with a very weak upper extremity is difficult. There is a shortage of technologies that successfully address this problem of too low a dose of arm movement, especially among the large population of stroke survivors with more severe deficits. The goal of this study is to test a new lever drive movable wheelchair arm rest device that facilitates a person performing high amounts of practice with the severely impaired upper extremity (UE) during early stroke recovery. We will randomize a total of 58 individuals with a subacute stroke to exercise using a movable wheelchair arm rest device or receive additional conventional therapy during their inpatient stay, in addition to their normal rehabilitation. We hypothesize that the individuals who use the movable wheelchair arm rest device to exercise the arm will improve a measure of their upper extremity movement ability more than the control group as assessed at a follow-up evaluation.

---

### Background & Purpose of Research

## Describe the purpose, specific aims or objectives and specify the hypotheses or research questions to be studied:

For this study, we hypothesize that use of movable wheelchair arm rest device during inpatient therapy will lead to significantly greater improvements in UE motor recovery than conventional treatment. (For a demonstration video of the movable wheelchair arm rest device, please visit: <https://youtu.be/RfbaOGhJfug>). Our Aim is to perform a randomized controlled trial of the movable wheelchair arm rest device with inpatients with subacute stroke in three different inpatient rehabilitation facilities (N=58; Months 6-24). UCI will be one of the study sites. Rancho Los Amigos Rehabilitation center and Casa Colina Hospital and Centers for Healthcare will potentially be the other two study sites. We are in the process of negotiating the contracts between sites. Participants will be >3 days and <3 weeks post-stroke, with initial FM scores <4239. Participants will be randomized to receive the movable wheelchair arm rest device or an electronic exercise program and instructed to practice moving their arm between therapy sessions. The primary outcome measure will be change in FM score from baseline to three-months post-stroke. We hypothesize that participants who receive movable wheelchair arm rest device will have significantly greater improvements in FM score than control ( $p < 0.05$ , RM-ANCOVA) without an increase in pain or spasticity, if they exceed the putative threshold of UE motor drive needed for recovery. Success Criteria: A significantly greater increase in FM of >4.25 points (the FM MCID40) between movable wheelchair arm rest device and control at three months.

At project end, we will have validated the clinical feasibility and efficacy of the movable wheelchair arm rest device and optimized it for production and mass distribution. If our plan is successful, we will have demonstrated that wheelchair-based "rocking therapy" can help patients routinely achieve the threshold level of sensory motor drive needed to provoke true UE recovery.

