## **Describe the statistical methods for the stated specific aims and hypotheses. The analysis plans should match the stated study specific aims and hypotheses:**

All reported data from this study will be disaggregated by sex to test for any potential bias due to this biological variable. Data will be analyzed using modified intention-to-treat analysis. That is, all participants will be included in the analysis if the follow-up assessment is available, regardless of any deviations from the protocol. The effect of treatment on the primary outcome measure will be assessed using a repeated measures analysis of covariance (RM-ANCOVA) to account for any baseline differences between groups or variability in treatment intensity, with follow-up comparisons performed using Bonferroni-corrected t-tests or Wilcoxon rank sum tests if the data violates the assumption of normality. We hypothesize the participants in the movable wheelchair arm rest device group will have significantly greater and clinically meaningful (i.e. >4.25 FM points) reductions in motor impairment than participants in the control group due to the increased dose of UE motor system activation. Using data from the sensors on movable wheelchair arm rest device, we will test if this effect depends nonlinearly on the number of repetitions performed with the device, consistent with recent meta-analyses of forelimb recovery in a rodent model of stroke. That is, we hypothesize that the movable wheelchair arm rest device will provide a benefit only if the dose exceeds a threshold. A key goal is to also identify that threshold (by making a graph for humans like the one for rats), which will enable us to move forward with effective clinical prescription and goal setting with the movable wheelchair arm rest device. Visual analog pain, spasticity, and FAC scores will also be analyzed using RM-ANCOVA to test for significant changes related to use of the device. All analyses will be reviewed by a statistical consultant in the Institute for Clinical and Translational Science at UC Irvine.

**Provide precise definitions of the study endpoints and criteria for evaluation; if the primary outcomes are derived from several measurements (i.e., composite variables) or if endpoints are based composite variables, then describe precisely how the composite variables are derived:**

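### The efficacy hypothesis is stated both with and without a dose-threshold condition that arises after randomisation and has no stated value, so it is unclear which claim is confirmatory

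*Combined protocol and SAP*

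**What the plan says.** The Background & Purpose answer on aims and hypotheses states the efficacy claim in two ways.

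- **Unconditional.** It opens with the claim that "use of movable wheelchair arm rest device during inpatient therapy will lead to significantly greater improvements in UE motor recovery than conventional treatment". Its success criterion is "A significantly greater increase in FM of >4.25 points" for device against control at three months. Neither mentions dose.
- **Conditional.** Between these two, the sentence that names p < 0.05 and RM-ANCOVA limits the claim to participants "if they exceed the putative threshold of UE motor drive needed for recovery".

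The statistical methods answer under Study Design & Statistics has the same mixture.

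- **By arm.** The analysis is modified intention-to-treat: "all participants will be included in the analysis if the follow-up assessment is available, regardless of any deviations from the protocol". The hypothesis is also put by group: "We hypothesize the participants in the movable wheelchair arm rest device group will have significantly greater and clinically meaningful", with the 4.25-point margin.
- **By threshold.** It then says "we hypothesize that the movable wheelchair arm rest device will provide a benefit only if the dose exceeds a threshold", and adds "A key goal is to also identify that threshold", by means of a graph.
- **Model.** The RM-ANCOVA is meant to account for baseline differences or "variability in treatment intensity".

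The Non-Technical Summary and the Sample Size Determination are by arm, with no dose condition. No section gives the threshold a value. The 1000 repetitions a day in the device-group description is called a target dose and is not identified with the threshold.

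**The concern.** How many repetitions a participant performs is decided after randomisation, by the participant as well as by the allocation. A claim limited to those who pass a dose level is therefore not protected by randomisation: if people with better prospects also practise more, high users can outgain controls even if the device does nothing. The threshold is also to be found in the same data whose result it qualifies, which adds a search over cut-offs.

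The opposite risk concerns a null result. If benefit is expected only above an unstated level, a failed by-arm comparison can be put down to too few participants reaching it, and no value was fixed in advance to check that against. What is at stake is which statement the trial may report as its confirmatory conclusion.

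**Working it through.** **1. Which statements carry the condition**

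| Place | Dose condition? |
|---|---|
| Non-Technical Summary, hypothesis | No |
| Background & Purpose, opening sentence | No |
| Background & Purpose, sentence naming the test and p < 0.05 | Yes |
| Background & Purpose, success criterion | No |
| Sample Size Determination | No |
| Statistical methods, analysis population | No |
| Statistical methods, 4.25-point hypothesis | No |
| Statistical methods, dose-response hypothesis | Yes |
| Methods for the primary outcome (t-test or Wilcoxon) | No |

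Nothing says which version governs.

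**2. What the sample size supports**

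Inputs from Sample Size Determination: 29 per arm, 80% power, α = 0.05 (taken as two-sided), 10% dropout. Effect and SD are not given, so the 29 can only be solved backwards.

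- Evaluable per arm: 29 × 0.9 = 26.1, about 26.
- Implied standardised effect: (1.96 + 0.84) × √(2/26) = 0.777.
- If the effect is 4.25 points, the implied SD is 4.25 / 0.777 = 5.5 points.

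This is power for the by-arm contrast.

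**3. By-arm power if benefit really occurs only above a threshold**

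Assume an effect of 0.777 SD in the share f of device participants above it, and zero in the rest. With √(2/26) = 0.277, power = Φ(0.777f / 0.277 − 1.96).

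| f (assumed) | 100% | 75% | 50% | 25% |
|---|---|---|---|---|
| By-arm power | 80% | 56% | 29% | 10% |

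A null by-arm result would then be likely, and the conditional wording would be there to explain it.

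**4. Illustration: a dose-selected comparison with no device effect**

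Assumptions: 26 per arm; dose and FM gain bivariate normal with correlation ρ in the device arm; upper half by dose (13) against all 26 controls; rejection counted only in favour of the device (nominal 2.5%). The documents give no value for ρ.

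The upper half of a normal dose distribution averages √(2/π) = 0.80 SD above the mean, so the expected bias is about 0.80ρ, slightly less with 26 people. The standard error is √(1/13 + 1/26) = 0.340. Using the simulated bias, the false-positive rate is roughly 1 − Φ(1.96 − bias / 0.340).

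| ρ | Simulated bias (SD) | By formula | Simulated, upper half | Simulated, best of 6 cut-offs | Simulated, full arms |
|---|---|---|---|---|---|
| 0 | 0.00 | 2.5% | 2.5% | 6.4% | 2.5% |
| 0.2 | 0.153 | 6.6% | 6.3% | 13.9% | 2.4% |
| 0.3 | 0.235 | 10.2% | 10.0% | 20.0% | 2.5% |
| 0.5 | 0.386 | 20.5% | 20.5% | 36.9% | 2.5% |

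Separate runs put the upper-half figure at about 7% to 21% for ρ from 0.2 to 0.5. Allowing any cut-off that keeps at least 6 users gives about 16% to 43%. The full-arm comparison keeps its error rate throughout.

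**5. Dose in the primary model**

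Achieved intensity is also a post-randomisation variable. If it enters the RM-ANCOVA, it brings dose conditioning into the primary test even with the threshold clause removed. The Project Procedures description makes length of stay a covariate; that too is known only after randomisation.

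**The case against.** A reader might infer that the primary hypothesis applies only to participants above the threshold, and that the trial is therefore either biased or impossible to refute. The documents do not support that. Most statements of the hypothesis, the power statement, the analysis population and the success criterion compare the arms with no dose condition. That comparison can fail against a stated margin, and it holds its error rate.

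Nor does any section plan to compare above-threshold users with controls. The dose question is described as a test of nonlinear dependence on repetitions, using the device's sensors. The false-positive rates above belong to a contrast that the wording permits but does not prescribe. They also rest on assumed correlations. Therapists set the range of motion that counts as a repetition to each patient's ability, and the plan stratifies on FM and adjusts for baseline; each could weaken a link between dose and prognosis.

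A reader might also infer that dose is unobserved in controls. That is not so: the secondary outcomes and the list of data collection tools include repetitions with the device or the exercise program, and control exercise time is to be logged. What remains is that the logging described for controls is opening time, not repetitions, so a device threshold has no clear equivalent there.

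Finally, the clause can be read as a premise about mechanism, since the background calls the threshold a working hypothesis. That is fair, but it sits in the sentence that names the test and significance level, where a confirmatory claim is normally read.

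**Conclusion.** The concern holds as an inconsistency. The efficacy hypothesis appears with and without a post-randomisation condition, the condition has no value, and the trial's own data are to supply one. The planned by-arm analysis and the 4.25-point criterion stand. The fault is that a dose-selected result, or an appeal to dose after a null, could each be presented as consistent with the stated hypothesis.

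The size is conditional. The 7% to 21% and 16% to 43% figures assume no device effect, 26 per arm, a dose-gain correlation of 0.2 to 0.5, and a comparison the plan does not specify. The fall in by-arm power to 29% assumes that half the device arm passes the threshold and the other half gains nothing. None of these assumptions can be checked from the documents.

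This is a clarification to make before the analysis is finalised, and does not invalidate the trial. The renewal form makes it timely: enrolment is closed, analysis is under way, and 37 participants are recorded (22 men and 15 women) against 58 planned, so a null by-arm result is more likely than the design assumed.

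**What to change.** 1. In Background & Purpose, delete the threshold clause from the sentence that names the test and significance level.
2. Name the by-arm statement in the statistical methods answer as the only confirmatory hypothesis: all participants with a follow-up assessment, analysed in the arm to which they were randomised, whatever dose they reached.
3. Keep achieved dose or treatment intensity out of the primary model, and decide at the same time whether length of stay belongs there.
4. Label the threshold question exploratory, and specify its dose measure and estimation method.
5. State that a comparison of above-threshold users with controls is not evidence of efficacy, and that a non-significant by-arm result will be reported as no demonstrated benefit of assignment to the device.

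The cost is a change of wording, with no new data or visits. Because analysis has begun, the change should be dated, with a note of whether outcomes by arm had been seen. The threshold work is kept; what is given up is the option of using it to qualify the primary result.
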